	and Changes from Baseline (Baseline in OLE	Population
Table 14.3.4.3.1.5	Study) (Conventional Unit)	
	Creatinine Kinase Values and Changes from	
	Baseline (Baseline in OLE Study) (Conventional	Safety
Table 14.3.4.3.1.6	Unit)	Population
	Creatinine Kinase Values and Changes from	
	Baseline by Treatment and Baseline Estimated	Safety
	Glomerular Filtration Rate (eGFR) Category	Population
Table 14.3.4.3.1.7	(Baseline in OLE Study) (Conventional Unit)	
	HbA1C and Fasting Glucose Laboratory Values	
	and Changes from Baseline (Baseline in OLE	Safety
Table 14.3.4.3.1.8	Study) (Conventional Unit)	Population
	Serum Chemistry Laboratory Values and Changes	Safety
	from Baseline (Baseline in OLE Study) (Standard	Population
Table 14.3.4.3.2.1		

Confidential

Page 19 of 23

	Unit)	
	Hematology Laboratory Values and Changes from	Safety
Table 14.3.4.3.2.2	Baseline (Baseline in OLE Study) (Standard Unit)	Population
	Coagulation Laboratory Values and Changes from	Safety
Table 14.3.4.3.2.3	Baseline (Baseline in OLE Study) (Standard Unit)	Population
	Urinalysis Laboratory Values and Changes from	Safety
Table 14.3.4.3.2.4	Baseline (Baseline in OLE Study) (Standard Unit)	Population
	Alanine Aminotransferase (ALT), Aspartame	
	Aminotransferase (AST) and Total Bilirubin Values	Safety
	and Changes from Baseline (Baseline in OLE	Population
Table 14.3.4.3.2.5	Study) (Standard Unit)	
	Creatinine Kinase Values and Changes from	Safety
Table 14.3.4.3.2.6	Baseline (Baseline in OLE Study) (Standard Unit)	Population
	Creatinine Kinase Values and Changes from	
	Baseline by Treatment and Baseline Estimated	Safety
	Glomerular Filtration Rate (eGFR) Category	Population
Table 14.3.4.3.2.7	(Baseline in OLE Study) (Standard Unit)	
	HbA1C and Fasting Glucose Laboratory Values	Safety
	and Changes from Baseline (Baseline in OLE	Population
Table 14.3.4.3.2.8	Study) (Standard Unit)	Fopulation
	Estimated Glomerular Filtration Rate (eGFR)	Safety
	Values and Change from Parent Study (ETC-1002-	Population
Table 14.3.6.1.1	040) Baseline	Fopulation
	Estimated Glomerular Filtration Rate (eGFR)	Safety
	Values and Change from Baseline (Baseline in	Population
Table 14.3.6.1.2	OLE Study)	
	Shift Table of Estimated Glomerular Filtration Rate	Safety
	(eGFR) Category from Baseline of Parent Study	Population
Table 14.3.6.2.1	(ETC-1002-040) over the Study	
	Shift Table of Estimated Glomerular Filtration Rate	Safety
	(eGFR) Category from Baseline of OLE Study over	Population
Table 14.3.6.2.2	the Study	

Confidential

Page 20 of 23

	Shift Table of Urine Protein from Baseline of Parent	Safety
Table 14.3.6.3.1	Study (ETC-1002-040) over the Study	Population
	Shift Table of Urine Protein from Baseline of OLE	Safety
Table 14.3.6.3.2	Study over the Study	Population
	Post-Baseline of OLE Abnormal Liver Function	Safety
Table 14.3.6.4	Summary	Population
	Vital Signs Values and Changes from Parent Study	Safety
Table 14.3.7	(ETC-1002-040) Baseline	Population
	Vital Signs Values and Changes from OLE Study	Safety
Table 14.3.7.2	(ETC-1002-050) Baseline	Population
		All Enrolled
Listing 16.2.1	Patient Disposition	Patients
	Protocol Devictions	Safety
Listing 16.2.2	Protocol Deviations	Population
	Cardiovascular History and Cardiovascular Risk	Safety
Listing 16.2.3.2	Factors	Population
	Medical History from Parent Study ETC-1002-040	Safety
Listing 16.2.4.5	Medical History from Parent Study ETC-1002-040	Population
		Safety
		Population
		(Patients
	New Medical History during Rollover Period	Entered the
	New Medical History during Rollover Fehou	OLE Study
		beyond 30-Day
		Rollover
Listing 16.2.4.5.2		Window)
	Concomitant Non-statin Medications	Safety
Listing 16.2.4.6		Population
	Concomitant Statin Medications	Safety
Listing 16.2.4.7		Population
	Exposure	Safety
Listing 16.2.5.1		Population
Listing 16.2.5.2	IMP Administration	Safety

Confidential

Page 21 of 23

		Population
Listing 16.2.6.1	Lipids	FAS
	Adverse Events	Safety
Listing 16.2.7.1		Population
	Adverse Events Occurred during Rollover Period	Safety
	(Between End of Parent Study and Treatment Start	Population
Listing 16.2.7.1.2	of OLE Study)	
	Serious Adverse Events	Safety
Listing 16.2.7.2		Population
	Incremental Listing of Serious Adverse Events	Safety
Listing 16.2.7.2.1		Population
	Adverse Events Resulting in Withdrawal of IMP	Safety
Listing 16.2.7.3		Population
	Incremental Listing of Adverse Events Resulting in	Safety
Listing 16.2.7.3.1	Withdrawal of Study Drug	Population
	Related Treatment-emergent Adverse Events	Safety
Listing 16.2.7.4		Population
	Deaths	Safety
Listing 16.2.7.5		Population
	Incremental Listing of Deaths	Safety
Listing 16.2.7.5.1		Population
	Adverse Events of Special Interest	Safety
Listing 16.2.7.7	Adverse Events of Special Interest	Population
	Adjudicated Major Adverse Cardiovascular Events	Safety
Listing 16.2.7.8	and Mortality (MACE) and Non-MACE Events	Population
	Categorical Urinalysis Safety Laboratory	Safety
Listing 16.2.8.1.1		Population
	Chemistry Safety Laboratory	Safety
Listing 16.2.8.1.2		Population
	Hematology Safety Laboratory	Safety
Listing 16.2.8.1.3		Population
	Coagulation Safety Laboratory	Safety
Listing 16.2.8.1.4		Population

Confidential

Page 22 of 23

	Urinalysis Safety Laboratory	Safety
Listing 16.2.8.1.5		Population
	Safety Laboratory Abnormalities	Safety
Listing 16.2.8.1.6		Population
	Safety Laboratory Parameters of Interest	Safety
Listing 16.2.8.1.7		Population
	Direct Bilirubin Values in Subjects with Gilbert's	Safety
Listing 16.2.8.1.8	Disease	Population
		Safety
Listing 16.2.8.1.9.1	Serum Pregnancy Test	Population
		Safety
Listing 16.2.8.1.9.2	Urine Pregnancy Test	Population
~	Physical Examination	Safety
Listing 16.2.10		Population
		Safety
Listing 16.2.11	Vital Signs	Population
	Mean (+/- SE) Low-density Lipoprotein Cholesterol	Safety
Figure 14.2.1	(LDL-C) Values by Visit (Observed Data)	Population
	Mean (+/- SE) High-density Lipoprotein Cholesterol	Safety
Figure 14.2.2	(HDL-C) Values by Visit (Observed Data)	Population
	Mean (+/- SE) Non-High-density Lipoprotein	
	Cholesterol (Non - HDL-C) Values by Visit	Safety
Figure 14.2.3	(Observed Data)	Population
	Mean (+/- SE) Total Cholesterol (TC) Values by	Safety
Figure 14.2.4	Visit (Observed Data)	Population
v	Median (IQR) Triglycerides (TG) Values by Visit	Safety
Figure 14.2.5.2	(Observed Data)	Population
*	Mean (+/- SE) Apolipoprotein B (apo-B) Values by	Safety
Figure 14.2.6	Visit (Observed Data)	Population
 	Median (IQR) High-sensitivity C-reactive Protein	Safety
Figure 14.2.7.2	(hs-CRP) Values by Visit (Observed Data)	Population

Confidential

Page 23 of 23

Version 1.3, Dec 04, 2019 Statistical Analysis Plan

Statistical Analysis Plan Title: A MULTICENTER OPEN-LABEL EXTENSION (OLE) STUDY TO ASSESS THE LONG-TERM SAFETY AND EFFICACY OF BEMPEDOIC ACID (ETC-1002) 180 MG ETC-1002-050 **Protocol: Clinical Phase:** 3 ETC-1002 **Product:** Version (Date): Statistical Analysis Plan – Version 1.3 Status: Final Prepared by: 05 Dec 2019 20:04:026+0000 **REASON: I approve this document** f1330a26-8e65-4f1e-b28b-172f4186890d Date 05 Dec 2019 20:50:034+0000 **REASON: I approve this document** 50c1bf44-b336-4cd2-9be1-2cc2a4697aa0 Date 05 Dec 2019 20:26:002+0000 **REASON: I approve this document** b0785ee0d Date **Esperion Therapeutics** 05 Dec 2019 20:08:034+0000 **REASON: I approve this document** 4901ad6b-ef32-4d59-80a4-a17c1403b3b6 Date **Esperion Therapeutics** Confidential Page 1 of 27

Page 103 of 129

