#### Statistical Analysis Plan for Study 1002-050, Day 120 Safety Update Interim Analysis

An interim analysis for Day120 safety update will happen  $\geq 4$  months after the cutoff for the NDA submission (15-Mar-2019). The set of tables, listings and figures that were run for the NDA submission will be run again for the Day 120 safety update with additional tables and listings as described here. In addition, all of the subject incidence treatmentemergent adverse event (TEAE) tables as specified in the original SAP (dated as 05-Dec-2018), will be replaced with exposure-adjusted tables.

The lipid modifying treatment (LMT) use at the study baseline will be summarized by anatomic therapeutic chemical class and preferred term by treatment group in the parent study (1002-040) for the safety population.

The summary tables will be generated for incremental adverse events, serious adverse events, death, adverse events leading to discontinuation of investigational product and major adverse cardiac event by treatment group in the parent study (1002-040) for the safety population.

To calculate exposure-adjusted subject incidence, the number of subjects with at least one incidence of a given treatment-emergent adverse event (TEAE) will be used as the numerator, and the exposure-years for all the subjects for that treatment-emergent adverse event will be used as the denominator. The exposure-years will be calculated as total person time (in person-years) at risk from on or after the first dose of IMP and up to last date of IMP+30 days or end of study date or analysis cut-off date whichever is earlier for subjects who did not have a given TEAE. For a subject with the TEAE, the exposure-year will be calculated as total person time from on or after first dose of IMP to the onset date of first occurrence of the given TEAE. In the tables by maximum severity, the first occurrence to the maximum severity of the TEAE will be used for the exposure calculation.

The tables and listing	ngs for the Day	120 analyses:
------------------------	-----------------	---------------

Number	Title	Population
	Detient Dispesition	The Enrolled
Table 14.1.1.1	Patient Disposition	Patients
	Major Drate cal Deviation	Safety
Table 14.1.1.2	Major Protocol Deviation	Population
	Demographic and Baseline Characteristics from	Safety
Table 14.1.2.1	the Parent ETC-1002-040 Study	Population
	Demographic and Baseline Characteristics from	Safety
Table 14.1.2.1.1	OLE Study	Population

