Table 14.3.3.1.8	Exposure-Adjusted Incidence of Treatment- emergent Adverse Events by System Organ Class, Preferred Term and Maximum Severity	Safety Population – by Baseline Body Mass Index (BMI) Group
Table 14.3.3.1.9	Exposure-Adjusted Incidence of Treatment- emergent Adverse Events by System Organ Class, Preferred Term and Maximum Severity	Safety Population – by Region
Table 14.3.3.2.1	Exposure-Adjusted Incidence of Treatment- emergent Serious Adverse Events by System Organ Class, Preferred Term and Maximum Severity	Safety Population
Table 14.3.3.2.2	Exposure-Adjusted Incidence of Treatment- emergent Serious Adverse Events by System Organ Class, Preferred Term and Maximum Severity	Safety Population - by Gender
Table 14.3.3.2.3	Exposure-Adjusted Incidence of Treatment- emergent Serious Adverse Events by System Organ Class, Preferred Term and Maximum Severity	Safety Population - by Age
Table 14.3.3.2.4	Exposure-Adjusted Incidence of Treatment- emergent Serious Adverse Events by System Organ Class, Preferred Term and Maximum Severity	Safety Population – by Baseline CVD risk Category
Table 14.3.3.2.5	Exposure-Adjusted Incidence of Treatment- emergent Serious Adverse Events by System Organ Class, Preferred Term and Maximum Severity	Safety Population – by Baseline Statin Intensity

Confidential

Page 12 of 23

Table 14.3.3.2.6	Exposure-Adjusted Incidence of Treatment- emergent Serious Adverse Events by System Organ Class, Preferred Term and Maximum Severity	Safety Population – by Race
	Exposure-Adjusted Incidence of Treatment-	Safety
	emergent Serious Adverse Events by System	Population –
	Organ Class, Preferred Term and Maximum	by History of
Table 14.3.3.2.7	Severity	Diabetes
		Safety
	Exposure-Adjusted Incidence of Treatment-	Population –
	emergent Serious Adverse Events by System	by Baseline
	Organ Class, Preferred Term and Maximum	Body Mass
	Severity	Index (BMI)
Table 14.3.3.2.8		Group
	Exposure-Adjusted Incidence of Treatment-	Cofoty
	emergent Serious Adverse Events by System	Safety
	Organ Class, Preferred Term and Maximum	Population –
Table 14.3.3.2.9	Severity	by Region
	Exposure-Adjusted Incidence of Treatment-	
	emergent Adverse Events Resulting in	Safety
	Discontinuation of IMP by System Organ Class,	Population
Table 14.3.3.3.3	Preferred Term and Maximum Severity	
	Exposure-Adjusted Incidence of Treatment-	
	emergent Adverse Events of Special Interest	Safety
	(AESIs) by System Organ Class, Preferred Term	Population

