Treatment-emergent Adverse Events by System	
Organ Class and Preferred Term	by History of
-	Diabetes
	Safety
Exposure-Adjusted Incidence of Related	Population –
	by Baseline
	Body Mass
	Index (BMI)
	Group
Exposure-Adjusted Incidence of Related	Safety
Treatment-emergent Adverse Events by System	Population –
Organ Class and Preferred Term	by Region
Exposure-Adjusted Incidence of Related	Safety
-	Organ Class and Preferred TermExposure-Adjusted Incidence of Related Treatment-emergent Adverse Events by System Organ Class and Preferred TermExposure-Adjusted Incidence of Related Treatment-emergent Adverse Events by System Organ Class and Preferred TermExposure-Adjusted Incidence of Related Treatment-emergent Adverse Events by System Organ Class and Preferred TermExposure-Adjusted Incidence of Related Treatment-emergent Adverse Events by System Organ Class and Preferred TermExposure-Adjusted Incidence of Related Treatment-emergent Adverse Events by System Organ Class and Preferred TermExposure-Adjusted Incidence of Related Treatment-emergent Adverse Events by System Organ Class and Preferred TermExposure-Adjusted Incidence of Related Treatment-emergent Adverse Events by System Organ Class and Preferred TermExposure-Adjusted Incidence of Related Treatment-emergent Adverse Events by System Organ Class and Preferred TermExposure-Adjusted Incidence of Related Treatment-emergent Adverse Events by System

Confidential

Page 15 of 23

	Interest (AESIs) by System Organ Class and Preferred Term	
Table 14.3.3.6.3	Exposure-Adjusted Incidence of Related Treatment-emergent Serious Adverse Events by System Organ Class and Preferred Term	Safety Population
Table 14.3.3.6.4	Exposure-Adjusted Incidence of Treatment- emergent Adverse Events of Special Interest (AESIs) Resulting in Discontinuation of IMP by System Organ Class and Preferred Term	Safety Population
Table 14.3.3.7.1	Exposure-Adjusted Incidence of Treatment- emergent Adverse Events by Preferred Term	Safety Population
Table 14.3.3.7.2	Exposure-Adjusted Incidence of Treatment- emergent Serious Adverse Events by Preferred Term	Safety Population
Table 14.3.3.7.3	Exposure-Adjusted Incidence of Related Treatment-emergent Adverse Events by Preferred Term	Safety Population
Table 14.3.3.8.1	Exposure-Adjusted Subject Incidence of Treatment-emergent Adverse Events by System Organ Class and Preferred Term	Safety Population

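### The Day 120 exposure rule for tables by maximum severity ends time at risk according to a severity known only later, which biases some rates by severity

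*SAP*

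**What the plan says.** The rule is in the SAP addendum headed Statistical Analysis Plan for Study 1002-050, Day 120 Safety Update Interim Analysis. It has four parts.

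- **Numerator:** "the number of subjects with at least one incidence of a given treatment-emergent adverse event (TEAE) will be used as the numerator".
- **Denominator:** "the exposure-years for all the subjects for that treatment-emergent adverse event will be used as the denominator".
- **Patients without the event** contribute time from first dose "up to last date of IMP+30 days or end of study date or analysis cut-off date whichever is earlier".
- **Patients with the event** contribute "total person time from on or after first dose of IMP to the onset date of first occurrence of the given TEAE".

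One sentence then changes the last part for some tables: "In the tables by maximum severity, the first occurrence to the maximum severity of the TEAE will be used for the exposure calculation". I read this as time from first dose to the first event at the patient's own maximum severity.

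The addendum's table list shows where it applies. A typical title is "Exposure-Adjusted Incidence of Treatment- emergent Adverse Events by System Organ Class, Preferred Term and Maximum Severity". Exposure-adjusted tables with maximum severity in the title are 14.3.3.1.1 to 14.3.3.1.9 (TEAEs), 14.3.3.2.1 to 14.3.3.2.9 (serious TEAEs), 14.3.3.3.3 (TEAEs leading to discontinuation) and 14.3.3.4.1 to 14.3.3.4.9 (AESI): 9 + 9 + 1 + 9 = 28. Other tables are not split by severity and keep the first-occurrence clock, for example 14.3.3.8.1, "Exposure-Adjusted Subject Incidence of Treatment-emergent Adverse Events by System Organ Class and Preferred Term".

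The addendum does not say whether each severity row has its own denominator, how a patient with a milder event counts in a higher row, or whether there is a total row. It includes no table shells.

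**The concern.** Maximum severity is known only when follow-up ends. Take two patients with the same mild event on the same day. The one who has nothing worse stops accruing time that day, although still at risk of a severe event. The one who later has a severe event keeps accruing until then. A person-time rate needs a risk set defined by what has happened so far, and this one is defined by what happens later.

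The addendum replaces the patient-incidence TEAE tables of the SAP dated 05 December 2018 with exposure-adjusted ones, so these rates are how severity would be read in the Day 120 update. The sentence also leaves the calculation open: two programmers could follow it and report different severe rates from the same data.

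**Working it through.** The plan states no rate or figure for this point, so there is nothing to reproduce. I checked the rule by hand and then under assumed rates.

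**1. Hand example.** Four patients, each followed for 1.5 years: S1 mild at 0.25 and severe at 1.0; S2 mild at 0.25; S3 moderate at 0.5 and mild at 0.75; S4 no event.

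| Quantity | Person-years | Rate per 100 PY |
|---|---|---|
| Total, first-occurrence clock | 0.25 + 0.25 + 0.5 + 1.5 = 2.50 | 3/2.50 = 120.0 |
| Total, maximum-severity clock | 1.0 + 0.25 + 0.5 + 1.5 = 3.25 | 3/3.25 = 92.3 |
| Severe, time to first severe event | 1.0 + 3 × 1.5 = 5.50 | 1/5.50 = 18.2 |
| Severe, shared denominator | 3.25 | 1/3.25 = 30.8 |
| Severe, own denominator | 5.50 | 1/5.50 = 18.2 |
| Mild, own denominator | 0.25 + 3 × 1.5 = 4.75 | 1/4.75 = 21.1 |

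With its own denominator the severe row is exact, because having a maximum of severe is the same as ever having a severe event. The mild row is not: S1 had a mild event at 0.25 years but contributes 1.5 event-free years, only because of the later severe event.

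**2. Size across all TEAEs, closed form.** Assume independent constant rates for the first mild, moderate and severe event of 0.60, 0.35 and 0.06 per person-year, and T = 1.5 years. Let m(λ) = (1 − e^(−λT))/λ − T·e^(−λT), the time contributed by patients whose clock stops at that severity, averaged over all patients.

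- Probabilities of no severe, no moderate and no mild event: 0.9139, 0.5916, 0.4066.
- Person-years per patient on the maximum-severity clock: m(0.06) + 0.9139·m(0.35) + 0.9139·0.5916·m(0.60) + 0.9139·0.5916·0.4066·1.5 = 0.0636 + 0.2556 + 0.2050 + 0.3297 = 0.8539.
- Severe, shared denominator: 0.0861/0.8539 = 10.1 per 100 PY. Correct: 6.0. Error +68%.
- Total: 0.7802/0.8539 = 91.4 per 100 PY. Correct: 60 + 35 + 6 = 101. Error about −10%.

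With rates from 0.40/0.25/0.04 to 0.80/0.50/0.08 (64% to 87% of patients with any event at 1.5 years), the severe error runs from +48% to +87% and the total error from −5% to −16%. At 1.0 year the ranges are +33% to +63% and −2% to −8%.

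**3. Size by level of the table, simulation.** This allows repeated events: 60,000 patients per scenario, gamma frailty with variance 1, mild/moderate/severe mix 60/35/5% or 45/40/15%, follow-up 1.0 or 1.58 years (1.5 years plus 30 days). All of these are assumptions.

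| Events per 100 PY | Roughly | Total row, error | Severe row, shared denominator, error |
|---|---|---|---|
| 3 | a preferred term | 0.0% | +1% to +2% |
| 10 | a common preferred term | −0.1% to −0.2% | +4% to +7% |
| 40 | a system organ class | −1.0% to −2.6% | +14% to +24% |
| 200 | all TEAEs | −11% to −19% | +40% to +68% |

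With a denominator per row, the severe row showed no error in any scenario.

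**4. Which tables can be compared.** Tables not split by severity exist for 14.3.3.1.1 (14.3.3.8.1), for 14.3.3.2.1 (14.3.3.8.2) and for the preferred-term rows of 14.3.3.4.1 (14.3.3.7.1). The other 25, namely 24 subgroup tables and 14.3.3.3.3, have no listed counterpart.

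**The case against.** A reader might infer that the severe and total rates are wrong in all 28 tables and contradict the tables not split by severity. The documents do not support that.

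- The severe-row error needs one denominator for all rows. The denominator sentence points that way but does not rule out one per row, under which the severe row is correct.
- No total row is specified, so its error is conditional on the layout.
- A contradiction can arise only in two tables and part of a third, and only where a patient has a later, worse event.
- Nor is there a general lack of a sound rate. AESI are a fixed list of preferred terms (SAP Appendix 2), so their overall first-occurrence rates can be read from 14.3.3.7.1. Table 14.3.3.6.4 covers AESI leading to discontinuation, and TEAE and serious TEAE overviews by subgroup stay on the list.
- In 14.3.3.3.3 the clocks differ only if a patient has a second, worse event that also leads to discontinuation, which should be uncommon.
- The analyses are descriptive (protocol section 12.1), and the rule serves one interim. SAP version 1.3, section 5.4.1, plans counts and percentages by maximum severity without it.

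All of this stands and limits the scope. It does not remove the defect. Under either denominator at least the mild and moderate rates depend on later events, and the sentence is a stated rule that a programmer would have to follow. Any tabulation by maximum severity looks at the whole of follow-up. That is harmless for counts, but not for a rate whose person-time is cut by the same information.

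**Conclusion.** The concern holds in limited form. In 28 exposure-adjusted tables the addendum ends time at risk by reference to a severity that is known only afterwards. A shared denominator overstates the severe rate; a denominator per row gives a correct severe rate but misclassifies time in the mild and moderate rows. Any total row on this clock is understated.

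Under the assumed rates the error is material for a line covering all TEAEs, moderate for the severe row of a system organ class if the denominator is shared, and small for a single preferred term. These sizes rest on assumed event rates, severity mix, follow-up and between-patient variation; the direction does not. Patient counts and the final analysis in SAP version 1.3 are not affected. Because the protocol (section 12.4) allows exposure-adjusted rates where appropriate and only this addendum defines them, the rule should be corrected before it is reused.

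**What to change.** Replace the sentence on maximum severity in the addendum with a rule of this content:

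- Exposure-adjusted rates by severity are given for three thresholds: any; moderate or severe; severe.
- The numerator is patients with at least one TEAE at or above the threshold.
- Time at risk for those patients ends at their first such TEAE.
- All other patients, including those with only milder TEAEs, contribute full follow-up, to the earliest of 30 days after last IMP, end of study, or cut-off.
- Any total row uses first occurrence and is checked against its own unsplit table where one is listed: 14.3.3.8.1 for 14.3.3.1.1, 14.3.3.8.2 for 14.3.3.2.1, and 14.3.3.7.1 for the preferred-term rows of 14.3.3.4.1.

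In the hand example this gives 3/2.50 = 120.0, 2/(1.0 + 1.5 + 0.5 + 1.5) = 2/4.50 = 44.4 and 1/5.50 = 18.2 per 100 PY. Counts by maximum severity can stay, without a rate.

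The cost is a short text change, small changes to the table titles and a revised denominator program. No new data are needed. The severity rows become cumulative and no longer add up to the total, which a footnote should say.
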